SAEs/AESIs will be assessed for severity, causal relationship to VTP-850 or alternative aetiology by the sponsor and investigator. The onset and resolution dates of the event and medical care taken in response to the event will be documented. If the event has not resolved by the end of the trial, it will be documented as “ongoing” on the eCRF, however, follow-up of the SAE/AESIs should be attempted until resolved or the condition has stabilised. Information recorded on the eCRF must be substantiated in the source documents.

The SAE form should be completed with all information known at the time and reported per the SAE/AESIs reporting guidelines.

Likewise, fatal or life-threatening SAEs will have to be reported per the SAE reporting guidelines. If the Medical Monitor is required by the protocol or chooses to suspend enrolment, they shall immediately create a written memorandum for record to the trial file and telephonically notify the sponsor of this act.

Contact information for all safety personnel is contained in the Team Contact List, which will be stored at the trial centre in the Investigator Site File and maintained by the trial sponsor.

Investigators must not wait to collect additional information to fully document the event before notifying the Medical Monitor of an SAE/AESI. The initial notification should include the following (at a minimum):

- Protocol number and name and contact number of the investigator
- Participant identification
- Investigational product
- Event term

All SAEs/AESIs must be recorded on the SAE/AESI Report Form and sent to [REDACTED] via email [REDACTED] within 24 hours of awareness. Additionally, the investigator must submit any updated SAE data to Precision Safety within 24 hours of awareness.

Initial notification via telephone or email does not replace the need for the Investigator to complete, sign, and return the SAE/AESI report form within the designated reporting time frames.

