A change in severity of an AE will be recorded as a new AE with the outcome of the event prior to the change in severity stated as "change in severity". The onset and resolution dates will encompass the duration of each severity.

Note: It is important to distinguish between serious and severe AEs. Severity is a measure of intensity whereas seriousness is defined by the criteria in [Section A3.3](#).

Assessment of Causality

For all AEs reported in the eCRF, the investigator will determine a **causal relationship** to VTP-850.

A number of factors will be considered in making this assessment, including: 1) the temporal relationship of the event to the administration of VTP-850, 2) whether an alternative aetiology has been identified and 3) biological plausibility.

Causality of all adverse events should be assessed by the investigator using the following question:

"Is there a reasonable possibility that the adverse event may have been caused by VTP-850?"

- **YES (related):** There is a reasonable possibility that VTP-850 contributed to the AE
- **NO (not related):** There is no reasonable possibility that the AE is causally related to the administration of VTP-850. There are other, more likely causes and administration of VTP-850 is not suspected to have contributed to the AE

The investigator is required to provide an assessment of relationship of AEs to VTP-850 or trial procedures and determine causality. The sponsor and Medical Monitor can add another causality assessment to the investigator's causality. If the sponsor or the Medical Monitor disagrees with the investigator's causality assessment, the opinion of both the investigator, the sponsor and the Medical Monitor should be provided with the report.

Every effort should be made by the investigator to determine the existence of any pre-existing conditions (e.g., headache on trial Day 1 with onset prior to VTP-850 administration) that must be taken into consideration when assessing causal relationship of an AE. Pre-existing conditions should be recorded in the eCRF as medical history and substantiated by appropriate source documentation. Intermittent conditions such as headaches may be present on trial Day 1 but may

represent an AE if the intensity or duration of the event is worse than usual following trial intervention.

Assessment of Outcome

The outcome of the AE will be assessed as:

- Recovered/resolved
- Recovered/resolved with sequelae
- Not recovered/resolved
- Unknown
- Fatal

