6.7.2. Adverse Events

All AEs recorded on the eCRF will be coded using the MedDRA dictionary [version 25.1 or later]:

- Treatment-emergent AEs (TEAEs) are events with start date on or after the first dose of VTP-850 and reported as not starting before first treatment.
- Treatment-Emergent Serious AEs (TESAEs) will be defined as TEAEs regarded by the investigator as Serious = “Yes”.
- The relationship between a TEAE and VTP-850 is assessed as related or not related. A treatment-related TEAE will be defined as a TEAE considered by the investigator related to treatment.

- Assessment of AE severity / intensity will be based on the National Cancer Institute-Common Terminology Criteria for AEs (NCI-CTCAE⁴, version 5.0). Severe TEAEs are defined as TEAEs assessed as being “Grade 3 / Grade 4 / Grade 5” in intensity.
- TEAEs leading to discontinuation of treatment are defined as TEAEs where “Action Taken With Study Treatment” is indicated as “Drug Withdrawn”.

Adverse events will be summarized for the Safety Analysis Set by treatment group and overall as follows:

- An overview of TEAEs including the number and percentage of participants with at least one of each mentioned TEAE type:
 - Any TEAE
 - Leading to discontinuation of study treatment
 - Leading to death
 - Grade 1 severity (mild)
 - Grade 2 severity (moderate)
 - Grade 3 severity (severe)
 - Grade 4 severity (life-threatening or disabling)
 - Grade 5 severity (death related to TEAE)
 - Any study treatment-related TEAE
 - Leading to discontinuation of study treatment
 - Leading to death
 - Any serious TEAE
 - Leading to death
 - Any serious study treatment-related TEAE
 - Leading to death
- The number and percentage of participants reporting each TEAE and the count of number of events will be summarized by SOC and PT for the following types of TEAEs:
 - TEAEs
 - TEAEs Leading to Discontinuation of Study Treatment
 - TEAEs Leading to Death
 - TEAEs by Maximum Severity
 - Treatment-related TEAEs
 - Treatment-related TEAEs by Maximum Severity
 - Treatment-related TEAEs Leading to Discontinuation of Study Treatment
 - Treatment-related TEAEs Leading to Death
 - Serious TEAEs
 - Serious TEAEs Leading to Discontinuation of Study Treatment
 - Serious TEAEs Leading to Death
 - Study Treatment Related Serious TEAEs
 - Study Treatment Related Serious TEAEs Leading to Death

- Study Treatment Related Serious TEAEs Leading to Discontinuation of Study Treatment
-

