- The number and percentage of participants who died will be summarized by the primary reason of death.

In the above summaries, participants with more than one TEAE within a particular SOC are counted only once for that SOC. Similarly, participants with more than one TEAE within a particular PT are counted only once for that PT, respectively. Overall summaries of “Any TEAE” and “Any study treatment-related TEAE” will only include participants at the maximum severity.

For summaries by maximum severity, participants with multiple TEAEs within a particular SOC or PT will be counted under the category of their most severe TEAE within that SOC or PT. TEAEs with missing severity will be included in the counts of the ‘Number of Participants with at least one TEAE’, ‘System Organ Class’ and ‘Preferred Term’ rows of the summary but they will not be included in the counts by severity.

The following tables will also be presented by administration (i.e. ChAdOx1-PCAQ dose, 1st MVA-PCAQ dose, 2nd MVA-PCAQ dose, 3rd MVA-PCAQ dose), for TEAEs that start within 28 days of each administration (e.g. summarizing TEAEs which occurred from ChAdOx1-PCAQ dose up to the earliest of 1st MVA-PCAQ dose or 28 days following the first dose). The denominator will be the number of participants who have received that dose:

- TEAEs
- TEAEs by Maximum Severity
- Treatment-related TEAEs
- Treatment-related TEAEs by Maximum Severity
- Serious TEAEs
- Study Treatment Related Serious TEAEs

Summaries by SOCs and PTs will be sorted by SOCs alphabetically (MedDRA) and PTs within SOC by descending order of total incidence. Where preferred terms tie, PTs will be sorted alphabetically.

No statistical comparisons of AEs between treatment groups will be performed.

All AE data will be listed using the Safety Analysis Set. Treatment-emergence status will be flagged in the listing. The listing will present the relative start and stop day of the AE calculated relative to the first dose of treatment. If the AE is “Ongoing” it will be indicated as such in the listing and the relative stop day will not be calculated.

In addition, the following listings will be presented:

- Listing of Deaths
- Listing of Serious TEAEs
- Listing of AEs Leading to Discontinuation of Study Treatment

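### An AE that improves in grade after the next dose is counted as a new event of that dose, because the protocol splits AEs at each grade change and the SAP never links the pieces

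*Protocol*

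**What the plan says.** Protocol Appendix 3, A3.4 (Assessment of Intensity) sets the recording rule: "A change in severity of an AE will be recorded as a new AE". The rule covers improvement as well as worsening. On dates it adds: "The onset and resolution dates will encompass the duration of each severity". The record that ends at the grade change is marked by its outcome code, *change in severity*.

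SAP 6.7.2 defines treatment-emergent AEs (TEAEs) as "events with start date on or after the first dose of VTP-850" that are not reported as starting before treatment. It does not require a record to be a new episode. For TEAEs and their subtypes, the number of participants and "the count of number of events will be summarized by SOC and PT". A further set of tables is given by administration, "for TEAEs that start within 28 days of each administration". In the SAP's example the window after the prime runs "up to the earliest of 1st MVA-PCAQ dose or 28 days following the first dose". On the denominator it says: "The denominator will be the number of participants who have received that dose".

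Within a table, a participant is counted once per system organ class and once per preferred term. SAP 6.7.2 does not mention the *change in severity* outcome or any linking of records.

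**The concern.** The recording rule and the counting rule are each reasonable alone but do not fit together. The first cuts one clinical episode into several dated records. The second treats each record's start date as an onset and credits it to the most recent dose. If the cut falls after a later dose, a resolving event shows as an onset following that dose.

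Protocol 11.2.2.1 commits the trial to AE summaries for the 28 days after each administration. Investigators judge causality against VTP-850 as a whole (A3.4), so in the planned tables start date is the main thing that separates the prime from each boost. For improving events the error runs one way: it adds to the later dose and never removes from it. Safety is the primary objective, and the groups are small enough for one record to change a percentage visibly.

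**Working it through.** The plan states no figure for this point, so there is none to reproduce. The check applies the written rules to assumed AE histories.

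**Inputs.** Doses on Days 1, 29 and 57 (Protocol 4.1; SAP 2.1). One record per severity, dated by that severity (Protocol A3.4). Assignment by start date, with each window ending at the earlier of the next dose or 28 days (SAP 6.7.2; its example is for the prime, and I apply the same rule to the first boost). With on-schedule dosing, 1 + 28 = 29 and 29 + 28 = 57, so the windows run back to back. I assign a start on a dosing day to that day's dose.

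| Assumed episode | Records | Window of each record | Effect |
|---|---|---|---|
| A. Grade 2, Day 20 to 40, unchanged | 1 | Prime | None |
| B. Grade 2 from Day 20, Grade 1 from Day 31 | 2 | Prime; 1st MVA | Improvement credited to 1st MVA; event count 2 |
| C. Grade 2 from Day 20, Grade 1 from Day 25 | 2 | Prime; prime | Event count 2; dose correct |
| D. Grade 3 from Day 35, Grade 2 from Day 50, Grade 1 from Day 60 | 3 | 1st MVA; 1st MVA; 2nd MVA | Improvement credited to 2nd MVA; event count 3 |
| E. Grade 1 from Day 20, Grade 2 from Day 31 | 2 | Prime; 1st MVA | Worsening credited to 1st MVA, which may be intended; event count 2 |

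**Event counts.** An episode with k grade changes gives k + 1 records: k = 1 gives 2 (B, C, E) and k = 2 gives 3 (D). The once-per-term rule limits participants, not events.

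**By-dose incidence.** The once-per-term rule acts within each dose's table, so it does not stop the participant in B appearing under both the prime and the first MVA dose. The increment to that term under the later dose is 1/n, where n is the number who received that dose:

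- n = 3 (smallest Cohort 1): 1/3 = 33.3 points
- n = 6 (planned on-schedule number in Cohorts 2 and 3): 1/6 = 16.7 points
- n = 10: 1/10 = 10.0 points; n = 11: 1/11 = 9.1 points

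The larger values are an assumption. Protocol 1.1 and SAP 2.3 expect about 25 participants in Phase 1, including replacements. With 3 to 6 in Cohort 1, Cohorts 2 and 3 would average between (25 − 6)/2 = 9.5 and (25 − 3)/2 = 11 each, if all of them were boosted.

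If the participant already has that term in the later window, the increment is zero.

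**Whole-trial incidence.** In every case above the participant counts once for the term, at maximum severity. The result is the same with or without linking.

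**The case against.** The strongest reply is that few events qualify and nothing primary depends on them. An affected event must straddle a dose and also change grade in the next window. Protocol 6.11 delays dosing for moderate or severe acute illness, which removes many histories like B. Protocol 7.1 stops further dosing after a related AE that stays at Grade 3 or above for more than 72 hours, apart from certain laboratory abnormalities, so D could not arise from a related clinical AE. The primary endpoints and estimand use participant numbers and proportions over the AE period. All AEs are listed with relative start and stop days, so a reader could spot adjoining records. SAP 6.1 leaves table specifications to the shells, which were not available and might hold a counting rule.

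Most of this stands as a limit on size. The affected group is narrowed but not emptied: laboratory, chronic and unrelated events remain. A listing does not correct a table, and the SAP text as written produces the double credit.

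Three stronger readings are tempting, and the documents do not support them.

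- A reader might infer that any ongoing AE is credited again at the next dose. It is not: without a grade change there is one record and one start date (case A).
- A reader might infer that the primary safety results are inflated. They are not, because each participant counts once.
- A reader might infer that the possible cardiac signal after the first MVA boost (Protocol 2.3.1) is an artefact of this rule. Nothing shows that. The signal rests on a death and named events in two further participants; cardiac events and dyspnoea are AESIs with 24-hour reporting and narratives.

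**Conclusion.** The gap is real and limited. Followed as written, the plan counts one episode more than once in the event totals, and can present an improving event as a new onset after a later dose in the by-dose tables.

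Each affected participant moves one term's by-dose incidence by 1/n, about 9 to 33 percentage points over the assumed range n = 3 to 11, or by nothing if the term is already present in that window. This rests on the grade change falling inside the later dose's window and on the shells containing no linking rule. How many real events are affected cannot be computed from the documents.

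The point deserves correction before the tables are produced because the error for improving events has a fixed direction and the remedy is cheap.

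**What to change.** Add a derivation to SAP 6.7.2:

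1. Link contiguous records of the same event where the earlier record's outcome is *change in severity*, and count the linked set as one event.
2. In the by-dose tables, do not count a record that only continues an earlier event at a lower grade as a new onset.
3. If the grade rises after a later dose, keep the original onset under the earlier dose at the grade reached in that window. Show the worsening under the later dose at its new grade, flagged as worsening. Case E would then appear as Grade 1 under the prime and as a flagged Grade 2 under the first MVA dose.

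Step 3 matters. Simply joining records and giving the highest grade to the first onset would move post-boost worsening into the prime window and understate boost toxicity.

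The cost is a small extra derivation, plus manual review where the coded term changes with severity and matching on the term would fail. The outcome code is already collected, so no eCRF or protocol change is needed. The table shells should be checked for consistency, and the same rule carried into the separate Phase 2 SAP.

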12.4 Appendix 4: Contraceptive and Barrier Guidance

Participants should refrain from donating sperm during the trial for at least 65 days after the last dose of VTP-850

PLUS, either

- Be abstinent from heterosexual intercourse as their preferred and usual lifestyle (abstinent on a long-term and persistent basis) and agree to remain abstinent

OR

- Agree to use a male condom when having sexual intercourse with a woman of childbearing potential, and should also be advised of the benefit for a female partner to use a highly effective method of contraception as a condom may break or leak

12.5 Appendix 5: Abbreviations and Definitions

List of Abbreviations

| ABBREVIATION | DEFINITION |
|--------------|--|
| ADT | androgen deprivation therapy |
| AE | adverse event |
| AESI | Adverse event of special interest |
| BRCA | BReast CAncer gene |
| ChAdOx1 | chimpanzee adenovirus Oxford 1 |
| CI | confidence interval |
| CRP | C-reactive protein |
| CRS | cytokine release syndrome |
| CT | computed tomography |
| CTCAE | Common Terminology Criteria for Adverse Events |
| CNS | Central Nervous System |
| DLT | dose limiting toxicity |
| eCRF | electronic case report form |
| ELISpot | enzyme linked immunospot assay |
| IB | Investigator's Brochure |
| ICF | informed consent form |
| IEC | independent ethics committee |
| IM | intramuscular(ly) |
| IRB | institutional review board |
| IV | intravenous(ly) |
| MedDRA | The Medical Dictionary for Regulatory Activities |
| MFS | metastasis-free survival |
| MRI | magnetic resonance imaging |
| MVA | Modified Vaccinia virus Ankara |
| MVA-BN | Modified Vaccinia Ankara-Bavarian Nordic |
| PAP | prostatic acid phosphatase |
| PBMC | peripheral blood mononuclear cells |
| PCWG3 | Prostate Cancer Working Group 3 |
| PET | positron emission tomography |
| pfu | plaque forming units |
| PSA | prostate-specific antigen |
| PSMA | prostate specific membrane antigen |
| PT | preferred term |
| RECIST | Response Evaluation Criteria in Solid Tumours |
| RP2R | recommended Phase 2 regimen |
| SAE | serious adverse event |
| SAP | statistical analysis plan |
| SI | International System of Units |
| SMC | Safety Monitoring Committee |
| SoA | Schedule of Assessments |

| ABBREVIATION | DEFINITION |
|--------------|--|
| SOC | system organ class |
| STEAP1 | six-transmembrane epithelial antigen of prostate 1 |
| TTM | Time to Metastases |
| ULN | upper limit of normal |
| vp | viral particles |
| XRT | external radiation therapy |

List of Definitions

| TERM | DEFINITION |
|-----------|--|
| Enrolment | The point at which a participant has met all entry criteria and is eligible for dosing. |
| VTP-850 | A prime-boost immunotherapeutic regimen consisting of 2 viral vectored components, ChAdOx1-PCAQ and MVA-PCAQ |

12.6 Appendix 6: Changes made in Protocol Amendment

This is Version 5.0 of the protocol. The original protocol (Version 1.0) was issued on 22 April 2022, Version 2.0 was issued on 01 July 2022, Version 3.0 was issued on 06 December 2022 and Version 4.0 was issued on 04 March 2024.

Summary of changes:

| Version 5.0 18 April 2024 | |
|---|--|
| Summary and Justification of Change | |
| 
The following changes were made in response to the request from the US Central IRB to minimise potential cardiac risks for trial participants:
 
 • Schedule of Assessments: addition of screening echocardiogram. A historic echocardiogram can be used if performed within 3 months of the first dose of VTP-850 • Table 3 Section 2.3.1: addition of echocardiogram in the cardiac risk statement • Addition of Section 8.4.5: echocardiogram • Section 9.5: included echocardiogram in the assessments that should be performed in the event of a cardiac-related event | |
| Version 4.0 04 March 2024 | |
| Summary and Justification of Change | |
| 
The following changes were made to increase participant safety, to minimise potential cardiac risks and to monitor cardiac status subsequent to safety review:
 
Cardiac safety:
 
 • Inclusion criterion 11: addition of inclusion criteria regarding troponin T and HbA1c • Exclusion criterion 12: increased exclusion of prior ADT from within 6 months prior to Day1 to outside of the primary prostate cancer therapy • Exclusion criterion 13: clarification that of the exclusion of receipt of experimental agents for prostate cancer includes participation in any clinical trials for prostate cancer with the exception of as being part of primary treatment options • Exclusion Criterion 19: addition of exclusion of participation in prior clinical trials to include previous participating in any clinical trials for prostate cancer with the exception of those as part of the primary treatment • Addition of exclusion criterion 20 detailing exclusionary cardiovascular conditions • Addition of exclusion criterion 21 detailing exclusionary ECG findings • Addition of exclusion criterion 22 specifying exclusion of uncontrolled hypertension | |

- Schedule of Assessments: Addition of on trial monitoring of ECGs
- Schedule of Assessment and Appendix 2: addition of troponin T and CRP analysis
- Schedule of Assessments, Section 9 (including addition of Section 9.5) and Appendix 3: Addition of classifying cardiac events as AESI and associated reporting
- Table 3 Section 2.3.1: Addition of cardiac risk statement
- Section 8.4.2: Addition that investigators should pay special attention to any symptoms or signs potentially pertaining to cardiotoxicity
- Section 8.4.3 and Appendix 2: clarification that Troponin T samples will be analysed in local laboratories

Other safety parameters:

- Addition of monitoring of anti-antigen antibodies

The following changes were made to increase homogeneity of participants and data collection:

Clarification of prostate cancer history:

- Inc 4 addition of "or systemic therapy for prostate cancer"
- Inc 6 addition of "and no evidence of prostatic bed recurrence"

Data consistency:

- Inc 6 removal of " An existing PSMA-PET scan showing no metastatic lesions may be used instead to confirm M0 status"
- Addition of a PSA collection at Day 91
- Section 4.1: addition that a total of 6 participants in each of cohorts 2 and 3 will be required to be dosed with MVA-PCAQ on Day 29 and Day 57 so participants whose dosing was delayed will be replaced (unless dosing not to be completed for pause or stopping rule criteria being met)
- Section 6.12: addition to detail how recommencement of dosing for participants whose dosing was delayed in Phase 1 due to a study pause will be managed

Clarification of the requirement to qualify sites for the collection of PBMCs as part of exploratory analyses:

- The collection of PBMC samples has changed from being required for all participants to only required at those sites that are qualified by Barinthus Biotherapeutics to process PBMC samples

The following changes were made for clarification:

- Exclusion criterion 4: clarification that history of Hep C infection is not exclusionary but in line with Ex 10 active Hepatitis C infection is exclusionary.
- Exclusion criterion 10: Updated to clarity that only active hepatitis C virus infection is exclusionary
- Update to SoA and associated footnotes following additional assessments

- Secondary Endpoint: rewording of endpoint regarding PSA response to ensure clarity
- Exploratory endpoint: moving "other immune responses" from the objective around PSA response to the objective around immunogenicity.
- Section 4.1 and Synopsis: clarification of the situation around when a participant could be offered an additional dose of MVA-PCAQ
- Section 4.1.2: clarification that if 3 or fewer of the 25 participants at the RP2R in Phase 1/ Phase 2 Stage 1 have a PSA response then no further participants will be enrolled in the trial
- Section 4.1.4: clarification that if a participant does not have a PSA response by their Month 6 visit they will not enter the Long-term Follow-up Period of the trial
- Section 4.1.7: clarification of how any additional MVA-PCAQ doses will be managed.
- Section 6.10: clarification that systemic treatment with corticosteroids or other immunosuppressive medications within 14 days of the first dose of VTP-850 are exclusionary.
- Section 7.2: clarification that disease management for example in the case of rapid PSA progression is a reason that the participant may need to discontinue from the trial to consider other treatment options.
- Section 8.2.2 clarification that participants with evidence of prostatic bed recurrence will be excluded from trial participation
- Section 8.3.2: clarification that biomarker samples will only be analysed after Phase 2 Stage 2 is opened. If Phase 2 Stage 2 is not opened then biomarker sample analysis may not be performed.
- Section 9.3: correction of "investigator safety report" to "individual case safety report" in bullets 3 and 4
- Section 11: minor updates to enhance clarity
- Section 11.3: addition of statement documenting the review of data of the 25 participants receiving RP2P to determine whether Phase 2 Stage 2 will be opened.
- Appendix 5: updated to include new abbreviations
- Administrative amendments to ensure internal consistency and correct typographical errors

In addition, Vaccitech (UK) Limited changed its name to Barinthus Biotherapeutics (UK) Limited on 06 November 2023. Consequent updates have also been made.

Version 3.0, 06 December 2022

Summary and Justification of Change

The following changes and clarification were made in response to FDA requests:

| |
|--|
| Addition of assessment of TTM in the subset of participants with PSA response to the secondary objectives and endpoints |
| Addition of assessment of MFS and TTM as exploratory objectives and endpoints 
• Revision of DLT criteria• Clarification of the staggering of enrolment during Phase 1 |
| Following feedback on current treatment paradigms in this population inclusion criterion 7 was amended so that participants who had prior prostatectomy should have a Serum PSA of >0.3 ng/mL at screening |
| Administrative amendments to ensure internal consistency and correct typographical errors |

Version 2.0, 01 July 2022

Summary and Justification of Change

Changes were made to:

- Amend inclusion criterion 3 to include participants that had undergone primary therapy for prostate cancer with brachytherapy.
- Amend inclusion criterion 7 to document that participants that had prior brachytherapy should have a serum PSA of 2ng/mL above nadir.
- Section 4.1.1 to reorder and slightly reword DLT criteria to improve clarity
- Include Investigator Agreement within the protocol

Remove previous legal registered address of sponsor (current legal address was already listed)

Section 8.3.1 included statement that left over immunology blood samples may, with participant consent, be retained for future research related to ChAdOx1-PCAQ and MVA-PCAQ, confirming that this additional consent is optional, will not be required for participation in the trial and may be withdrawn at any time.

Clarified that SMC will also contain a prostate cancer physician who is not participating in the trial

- Add summary of changes Appendix 6

Administrative amendments to ensure internal consistency and correct typographical errors
